**Table 11–1: Clinical laboratory measurements**

Category	Panel	Variable
Serology	Serology	human immunodeficiency virus (HIV), Hepatitis B and C, human leukocyte antigen (HLA)-B27 (HLA-B27)
Hematology	Red blood cell	red blood cell count a , hemoglobin a , hematocrit
	Red blood cell indices	mean corpuscular hemoglobin, mean corpuscular hemoglobin concentration, mean corpuscular volume
	Platelet	Platelet
	White blood cell	white blood cell count a
	White blood cell differential	Absolute counts: absolute neutrophils a , basophils, eosinophils, absolute lymphocytes, monocytes; atypical lymphocytes Percentages: neutrophils/leukocytes a , basophils/leukocytes a , eosinophils/leukocytes a , lymphocytes/leukocytes a , monocytes/leukocytes a .
Chemistry	Electrolytes	Sodium, chloride, potassium, magnesium, total calcium, bicarbonate

**Table 11–1: Clinical laboratory measurements**

Category	Panel	Variable
	Kidney function	BUN, creatinine, uric acid, glomerular filtration rate
	Proteins	hs-CRP bc
	Liver function	AST a , ALT a , GGT a , ALP a , LDH a , total bilirubin, direct bilirubin (if indicated), indirect bilirubin (if indicated)
	Lipids	Total cholesterol a
	Hormones	FSH (postmenopausal females only)
	Fertility	Pregnancy test d
	Substrates	Glucose
Urinalysis	Dipstick	pH, albumin, glucose, blood (RBC, WBC)
	Urine sediment	RBC, WBC, crystals, bacteria

ALP=alkaline phosphatase; ALT=alanine aminotransferase; AST=aspartate aminotransferase; BUN=blood urea nitrogen; GGT=gamma glutamyl transferase; FSH=follicle stimulating hormone; HIV=human immunodeficiency virus; HLA-B27= human leukocyte antigen B27; hs-CRP=high sensitivity C-reactive protein; LDH=lactate dehydrogenase; RBC=red blood cell; WBC=white blood cell

a Shift tables will be presented for these variables.

b hs-CRP will be included in the listings and tabulations for the efficacy data and will not be included in the safety data outputs.

c hs-CRP will be tested at specified visits per the study schedule of events.

d Serum pregnancy test to be performed at Screening; urine pregnancy test to be performed at subsequent.

## 11.4 Vital signs, physical findings, and other observations related to safety

### 11.4.1 Vital signs

The following vital signs measurements will be obtained:

- Pulse rate
- Systolic and diastolic blood pressure
- Temperature

A by-subject listing of all vital sign measurements and changes from Baseline will be presented by treatment group and visit. The listing will include a flag for measurements identified as TEMA/potentially clinically significant (PCS) as calculated by the criteria outlined in [Table 14–8](#). Body weight will be included in the listing.

Descriptive statistics will be reported for all vital sign measurements. Observed values and changes from Baseline will be summarized by treatment group for each vital signs variable and visit.

Figures of mean change from Baseline over time will be presented for each variable by treatment group.

The number and percentage of subjects with TEMA/PCS vital sign values will be summarized by treatment group at each visit. The denominator for the percentages will be the number of subjects with a non-missing measurement for the variable at the specific visit.

#### **11.4.2      ECG**

The following ECG variables will be reported together with the Investigator's interpretation of the ECG profile:

- PR interval
- RR interval
- QRS interval
- QT interval
- Heart rate
- QT corrected for heart rate using Fridericia's formula (QTcF)

Electrocardiogram results will be reported in the by-subject listings. The listing will also include the changes from Baseline and percentage changes from Baseline and will be presented by treatment group and visit.

Observed results, changes and percentage changes from Baseline will be summarized for each ECG variable by treatment group and visit.

The following cut points in QTcF (observed data and change from Baseline) will be summarized categorically by treatment group (number and percentage of subjects) and visit. The denominator for the percentages will be the number of subjects with a non-missing measurement for the variable at the specific visit.

Observed QTcF data:

- <450msec
- $\geq 450$ msec to <480msec
- $\geq 480$ msec to <500msec
- $\geq 500$ msec

Change from Baseline in QTcF:

- <30msec
- $\geq 30$ msec to <60msec
- $\geq 60$ msec

Electrocardiogram findings including the Investigator's interpretation will be listed separately.

#### **11.4.3 Other safety variables**

##### **11.4.3.1 C-SSRS**

The C-SSRS is divided into 2 time intervals and further sub divided as shown:

- C-SSRS at Baseline – assessed at the Screening visit
  - Suicidal Ideation – over Lifetime and over Past 6 Months
  - Intensity of Ideation – over Lifetime and over Past 6 Months
  - Suicidal Behavior – over Lifetime and over Past 2 Years
- C-SSRS Since Last Visit – assessed at all visits after Screening
  - Suicidal Ideation – Since Last Visit
  - Intensity of Ideation – Since Last Visit
  - Suicidal Behavior – Since Last Visit

For Suicidal Ideation questions, only those questions where "Yes" has been answered will be listed. For Intensity of Ideation questions and Suicidal Behavior questions, any question for which an answer has been recorded will be listed.

Results, as specified above, will be listed by treatment group, subject and visit.

##### **11.4.3.2 Physical examination**

Subjects with abnormalities in the physical examination will be listed including details of the abnormality.

##### **11.4.3.3 Chest X-ray/CT scan and TB questionnaire**

The results of the chest X-ray and the TB questionnaire will be listed for each subject.

## **12 OTHER ANALYSES**

Not applicable.

## 14 APPENDICES

[figure not shown]
### 14.1 Bath Ankylosing Spondylitis Disease Activity Index

The BASDAI is shown in [Table 14-1](#). All questions are answered on a scale from 0 to 10; for questions 1 to 5, 0 = none and 10 = very severe; for question 6, 0 = 0 hours, 10 = 2 or more hours.

### 14.2 Bath Ankylosing Spondylitis Functional Index

The BASFI is shown in [Table 14-2](#). All items are scored on a scale from 0 (“Easy”) to 10 (“Impossible”). The first 8 items evaluate activities related to functional anatomical limitations due to ankylosing spondylitis and the final 2 items evaluate a subject's ability to cope with everyday life.

### 14.3 Hospital Anxiety and Depression Scale

The individual items on the HADS-A and HADS-D scales are listed in [Table 14-3](#).

### 14.4 Treatment group assignment for the TFLs

Data will be summarized in the TFLs according to the treatment groupings as displayed in [Table 14-4](#).

**Table 14-4: Treatment group assignment for TFLs**

TFL group	CZP	BKZ	All Subjects
Subject disposition	X	X	X
Protocol deviations	X	X	X
Demographics	X	X	X
AS history and Baseline Disease characteristics	X	X	X
Medical history	X	X	X

**Table 14–4: Treatment group assignment for TFLs**

TFL group	CZP	BKZ	All Subjects
Prior/concomitant medications	X	X	X
AEs	X	X	
Safety data (including vital signs, ECG, laboratory tests, physical examination, body weight, C-SSRS)	X	X	
Pharmacodynamic data	X	X	
Efficacy data	X	X	
Pharmacokinetic data	X	X	
ADA	X	X	

ADA= anti-drug antibodies; AE=adverse event; C-SSRS=Columbia-Suicide Severity Rating Scale; ECG=electrocardiogram

## 14.5 Adverse events for special monitoring

The following AESM are defined for BKZ and will be summarized separately as described in [Section 11.2](#):

- Major cardiovascular events
- Serious infections, including opportunistic infections and TB
- Malignancies including lymphoma
- Cytopenias
- Neuropsychiatric events
- Inflammatory bowel disease
- Anaphylactic reaction (hypersensitivity and anaphylactic reactions)
- Hepatic events and drug-induced liver injury

### 14.5.1 Major cardiovascular events

Major adverse cardiovascular events (MACE) will be tabulated separately and will be identified using the following UCB-defined search criteria:

- All serious TEAEs which code to a PT included in the Scope=Broad and/or Scope=Narrow groups of the following standardized MedDRA queries (SMQ):
  - Haemorrhagic central nervous system vascular disorders
  - Ischaemic central nervous system vascular disorders

- All serious TEAEs which code to a PT included in the HLT = 'Ischaemic coronary artery disorders' except events coding to PT = 'Chest pain' or PT = 'Chest discomfort'
- All serious TEAEs which code to a PT = 'Cardiac failure congestive'

#### **14.5.2      Serious infections, including opportunistic infections and tuberculosis**

##### **14.5.2.1    Serious infections**

Serious infections are based on MedDRA classification using the SOC = 'Infections and Infestations'. Such events will be included in the tabulations of SAEs and no separate summary tabulations will be presented.

##### **14.5.2.2    Fungal infections**

Fungal infections will be summarized separately based on all TEAEs coding to the high level group term (HLGT) = 'Fungal infectious disorders'.

##### **14.5.2.3    Opportunistic infections**

Opportunistic infections (including TB) will be summarized in a separate table including all TEAEs identified using search criteria defined by UCB.

Opportunistic infections are identified in 2 steps:

- Step 1: Refer to column B of the spreadsheet which identifies the PTs to be classified as opportunistic infections using either a single 'x' or a double 'xx'
  - All TEAEs which code to a PT flagged with a single 'x' need to also be serious in order to be considered an opportunistic infection
  - All TEAEs which code to a PT flagged with a double 'xx' are considered to be an opportunistic infection, regardless of seriousness.

All serious TEAEs in the study database which code to a PT flagged with a single 'x' and all TEAEs in the study database which code to a PT flagged with a double 'xx' will be summarized as an opportunistic infection in the stand-alone table.

- Step 2: Refer to column C of the spreadsheet which identifies the PTs that need to be evaluated on a case-by-case basis by the study physician in order to determine whether it is a true opportunistic infection or not. The process for physician review is as follows:
  - Study programming team creates a spreadsheet which lists all of the subjects with a TEAE present in the database which codes to a PT identified as needing case-by-case review. Information from the AE dataset to be included in the spreadsheet: Subject ID, AE verbatim term, SOC, HLT, Low Level Term (LLT), PT, AE start date, AE end date, seriousness, severity, relationship to IMP, action taken. Additionally, a column will be included where the study physician can document their decision on the case
  - Study physician reviews the cases in the spreadsheet and indicates in the additional column which AEs are confirmed to be opportunistic infections via a single 'x'

- Study programming team incorporates these decisions into the ADAE dataset by merging the study physician decisions for individual subjects / PTs and flagging the confirmed opportunistic infections as such in the dataset

All subjects with an AE reported that has been confirmed by the study physician to be an opportunistic infection (based on case-by-case review) will be summarized as such in the stand-alone table, together with all of the events identified in Step 1 of this process.

Following the initial physician review of case-by-case events, subsequent reviews will be based on the cumulative set of case-by-case events present in the database at each time point of spreadsheet creation. Physician decisions from previous runs should be retained in each subsequent run. The final run of the spreadsheet, with all study physician decisions on the full set of case-by-case events, will be archived at the end of the study.

#### **14.5.3 Malignancies including lymphoma**

Malignancies will be presented in 2 separate tables based on the following SMQs:

- Malignant or unspecified tumors
- Malignant tumors

Events included in the ‘Malignant tumors’ tabulation will be a subset of the events in the ‘Malignant or unspecified tumors’ tabulation. The SMQ search should include all TEAEs which code to a PT included in the Scope=Narrow group within each SMQ.

The output tables will include 2 different overall incidence rows:

- The first overall incidence row will summarize ‘Any malignancies (including unspecified)’ or ‘Any malignancies’ (depending on the table) and this row will summarize the incidence of all AEs flagged for inclusion in the table, regardless of the HLT it codes to
- The second overall incidence row will summarize ‘Any malignancy (including unspecified, excluding non-melanomic skin cancers)’ or ‘Any malignancy (excluding non-melanomic skin cancers)’ (depending on the table) and this row will summarize the incidence of AEs flagged for inclusion in the table, excluding those which code to an HLT of ‘skin neoplasms malignant and unspecified (excl melanoma)’

#### **14.5.4 Cytopenias**

Cytopenias will be tabulated separately based on the SMQ = ‘Haematopoietic cytopenias’. Only serious TEAEs will be included in the tabulation. The SMQ search should include all serious TEAEs which code to a PT included in the Scope=Broad and/or Scope=Narrow groups within the SMQ.

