12.1.1.3 Adverse events of special interest

An AE of special interest is any AE that a regulatory authority has mandated be reported on an expedited basis, regardless of the seriousness, expectedness, or relatedness of the AE to the administration of a UCB product/compound. Potential Hy's Law, defined as $\geq 3 \times \text{ULN}$ ALT or AST with coexisting $\geq 2 \times \text{ULN}$ total bilirubin in the absence of $\geq 2 \times \text{ULN}$ ALP, with no alternative explanation for the biochemical abnormality, must ALWAYS be reported to UCB as an AE of special interest (AESI) (ie, without waiting for any additional etiologic investigations to have been concluded). Follow-up information should then be reported if an alternative etiology is identified during investigation and monitoring of the subject.

In addition, events that are considered as Adverse Events of Interest for CZP include:

- Serious infections including opportunistic infections
 - Malignancies including lymphoma
 - Congestive heart failure
 - Demyelinating-like disorders
 - Aplastic anaemia, pancytopenia, thrombocytopenia, neutropenia and leucopenia

- Serious bleeding events
- Lupus and lupus-like illness
- Serious skin reactions (e.g. Stevens Johnson syndrome, toxic epidermal necrolysis, and erythema multiforme)

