12.1.1.4 Adverse events for special monitoring

UCB has identified AEs for special monitoring (AESM). An AESM is an AE or safety topic for which special monitoring, additional data collection activities, and/or enhanced signal detection activities (within UCB), are considered appropriate. Identified AESM can be of particular concern based on findings from the IMP clinical program to date, potential risks generally associated with biologic immunomodulators, or comorbidities and risk factors prevalent in the study population.

Adverse events for special monitoring for this study include: infections (serious, opportunistic, fungal, and TB, see [Section 12.7.5](#)), neutropenia, hypersensitivity, suicidal ideation and behavior (assessed using the C-SSRS), depression, (assessed using the HADS, see [Section 9.10](#)), major cardiovascular events, liver function test changes/enzyme elevations (ALT, AST, and bilirubin; see [Section 12.6.1](#)), malignancies, and inflammatory bowel diseases (with gastroenterology referral as appropriate).

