- Incidence of fatal TEAEs by relationship
- Incidence of non-serious TEAEs by relationship
- Incidence of serious TEAEs by relationship
- Incidence of non-serious TEAEs above threshold of 5% of subjects
- Incidence of non-serious TEAEs above threshold of 5% of subjects by relationship
- Incidence of TEAEs by SOC and PT (including the number and percentage of subjects and individual subject numbers for each PT stratified by intensity, relationship and seriousness)

[a] These summaries will be presented separately for TEAEs during the Treatment Period and TEAEs during the study.

[b] These summaries will be repeated for subjects in the SS who were randomized in the PET-MRI/PET-CT substudy and will be based on TEAEs during the study

In addition, separate summaries by treatment group, SOC, HLT and PT will be included for the following AEs for special monitoring (AESM):

- Major cardiovascular events
- Serious infections, including opportunistic infections and tuberculosis (TB)
- Malignancies including lymphoma
- Cytopenias
- Neuropsychiatric events
- Inflammatory bowel disease
- Anaphylactic reaction (hypersensitivity and anaphylactic reactions)
- Hepatic events and drug-induced liver injury

The criteria for identifying and additional criteria for reporting AESM are provided in [Section 14.5](#).

All summary tables (including those for AESM) will contain the number and percentage of subjects and the number of events where applicable. A subject who has multiple events in the same SOC, HLT and PT will be counted only once in the subjects counts but all events will be included.

In summaries including relationship to IMP, the following relationship categories will be included:

- Related
- Not related

Subjects who experience the same event multiple times will be included in the most related category for tabulations by maximum relationship. Events with missing relationship will be considered as 'Related' for summary purposes but shown as missing in the data listings.

In summaries including intensity, the following categories will be summarized:

- Mild
- Moderate
- Severe

Subjects who experience the same event multiple times will be included in the most severe category for tabulations by maximum intensity. Events with missing intensity will be considered as 'Severe' for summary purposes. All data will be presented as recorded in the database for the listings.

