#### **14.5.5 Neuropsychiatric events**

Neuropsychiatric events (in particular depression, anxiety and suicide ideation or behavior) will be tabulated separately based on the SMQ = ‘Depression and suicide/self-injury’. The SMQ search should include all TEAEs which code to a PT included in the Scope=Broad and/or Scope=Narrow groups within the SMQ.

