## **15 AMENDMENTS TO THE SAP**

### **15.1 Amendment 2**

#### **15.1.1 Rationale for the amendment**

Various updates were suggested with the introduction of the PET-MRI/PET-CT substudy, and to align with the changes made to protocol amendment 3.

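### The SAP's only special-monitoring table for neutropenia counts serious events alone, although the protocol sets no seriousness condition

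*SAP*

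**What the plan says.** Protocol 12.1.1.4 gives the AESM list in one sentence, which includes "neutropenia, hypersensitivity, suicidal ideation and behavior". Neutropenia carries no qualifier there. Infections in the same sentence do: "infections (serious, opportunistic, fungal, and TB".

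Protocol 12.1.1.3 separately lists events of interest for certolizumab pegol. One entry reads "Aplastic anaemia, pancytopenia, thrombocytopenia, neutropenia and leucopenia", again with no seriousness condition.

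SAP 11.2 promises separate summaries for each AESM topic, one of which is cytopenias, and states: "The criteria for identifying and additional criteria for reporting AESM are provided in" SAP 14.5. It also says that the adverse event listings will flag AESM.

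SAP 14.5.4 sets the rule for this topic. "Cytopenias will be tabulated separately based on the SMQ" for haematopoietic cytopenias, and then "Only serious TEAEs will be included in the tabulation". The search itself is also limited to serious TEAEs. No other AESM topic in SAP 14.5 covers neutropenia.

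**The concern.** The protocol tells the reader that neutropenia is watched specially, whatever its seriousness. The SAP output under that label answers a narrower question: how many subjects had a serious cytopenia of any cell line. A reader who goes to the AESM section for neutropenia could find an empty or nearly empty table although neutropenia had been reported as an adverse event.

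Safety and tolerability of bimekizumab is the trial's only secondary objective (Protocol 3.2), and the AESM tables are where the pre-named safety topics are brought together. The stake is the completeness of one safety summary and possibly of one listing flag. No efficacy analysis is touched.

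**Working it through.** Neither document states a figure on this point, so there is none to reproduce. The check is a comparison of texts, followed by arithmetic on assumed values to show the range.

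**Comparison of texts**

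1. Event named in the protocol: neutropenia, any seriousness (Protocol 12.1.1.4).
2. Event counted in the SAP's AESM table: serious TEAEs in the haematopoietic cytopenias query (SAP 14.5.4).
3. A non-serious neutropenia meets item 1 and fails item 2. The exclusion is complete for that class of event.
4. Does the protocol's wording support the filter, as it does for other topics? The serious-only rule in SAP 14.5.1 goes with a protocol term limited to major cardiovascular events, and SAP 14.5.2.1 goes with serious infections. For topics without such a word, the SAP does not limit the whole table to serious events. The neuropsychiatric rule in SAP 14.5.5 is an example: "The SMQ search should include all TEAEs which code to a PT included in the Scope=Broad and/or" narrow groups. Malignancies (14.5.3) likewise take all TEAEs in their search, and hepatic events (14.5.8) take all adverse events. Cytopenias stand apart: the whole table is limited to serious events, and nothing in the protocol term calls for it.
5. Does the topic label explain it? The amendment record in Protocol 19.5 shows that the earlier AESM term was cytopenias, which may be where the SAP's label comes from. That earlier term had no seriousness limit either, so the label's history does not account for the filter.

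**Share missed**

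Let s be the share of neutropenia TEAEs that are serious. The share missing from the table is 1 − s. The documents do not give s, so the values below are assumptions.

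| Assumed s | Missed (1 − s) |
|---|---|
| 5% | 95% |
| 10% | 90% |
| 25% | 75% |
| 50% | 50% |
| 100% | 0% |

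**Chance that no serious neutropenia reaches the table**

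Inputs: N = 72, the minimum total in SAP 2.4; p, the assumed proportion of subjects with any neutropenia TEAE; and s, read here as the share of those subjects whose event is serious. Subjects are taken as independent. Expected number with an event = N·p; expected number in the table = N·p·s; chance of none in the table = (1 − p·s)^72.

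| p | s | N·p | N·p·s | Chance of none in table |
|---|---|---|---|---|
| 2% | 5% | 1.44 | 0.07 | 93% |
| 5% | 10% | 3.6 | 0.36 | 70% |
| 5% | 50% | 3.6 | 1.8 | 16% |
| 10% | 25% | 7.2 | 1.8 | 16% |

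**Hypothetical single case**

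With 2:1 randomization, two thirds of 72 is 48 bimekizumab subjects. If 4 of the 48 had neutropenia and none was serious, an all-seriousness row would show 4/48 = 8.3% and the planned table would show no neutropenia. This shows how the filter works and is not a forecast.

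**The case against.** The strongest reply is that nothing is lost. SAP 11.2 tabulates all TEAEs by system organ class, high level term and preferred term. It tabulates non-serious TEAEs separately, also by relationship and above a 5% threshold. SAP 11.3 adds markedly abnormal neutrophil counts (below 1.0 × 10^9/L, Table 14-5), shift tables and figures of the mean neutrophil count. This stands, and it limits the point to the AESM outputs. It does not remove it. Preferred-term rows cannot be added up to a subject count if a subject has more than one term, and the laboratory outputs classify counts, not reported adverse events. None of them gives a grouped, subject-level count of neutropenia TEAEs under the AESM label.

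A second reply is that a seriousness filter is a sponsor convention: it applies to major cardiovascular events and to some opportunistic infection terms (SAP 14.5.2.3). That is a fair description, but for neutropenia the protocol wording gives it no footing.

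Two stronger readings are tempting, and the documents support neither.

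- A reader might infer that the table will miss nearly all neutropenia. No serious share is given. Protocol 12.1.1.2 also names blood dyscrasias without hospital admission as a possible important medical event, so neutropenia can be classed as serious without admission.
- A reader might infer that the SAP hides a departure which SAP 3.9 should have declared. SAP 3.9 covers changes to analyses the protocol defines, and Protocol 15.8.1 defines no AESM table. Likewise, the statement in SAP 15.1.1 that SAP amendment 2 was meant "to align with the changes made to protocol amendment 3" does not promise that every AESM search rule was revised.

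**Conclusion.** The mismatch is real and modest. Followed as written, SAP 14.5.4 keeps every non-serious neutropenia out of the only AESM table that covers the topic. Whether the listing flag is affected depends on its being built from the same criteria; the wording of SAP 11.2 makes this likely but does not say so outright.

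That conclusion rests on the two texts alone and needs no incidence figure. Its numerical size cannot be fixed from the documents: the 0% to 95% range follows entirely from the assumed serious share. The events remain visible in the general TEAE tables and, as low counts, in the laboratory outputs. The consequence is an AESM summary that can understate neutropenia, and the report as a whole still contains the data.

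**What to change.** In SAP 11.2 and 14.5.4:

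- Add neutropenia as an AESM topic, state which preferred terms count, and tabulate all such TEAEs regardless of seriousness by treatment group, with serious events as a sub-row.
- Apply the same criteria to the AESM flag in the adverse event listings.
- Keep the serious cytopenia row if it is wanted for other cell lines, labelled as serious only.

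The cost is one table filter and one flag rule. The data are already collected and coded, and no other analysis changes.
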